6.6 Anticoagulants

Rucaparib is a weak inhibitor of CYP2C9 in vivo. Caution should be exercised in patients receiving rucaparib and concomitant warfarin (Coumadin). Patients taking warfarin should have international normalized ratio (INR) monitored regularly per standard clinical practice.

6.7 Luteinizing Hormone-releasing Hormone Analogs

For prostate cancer patients who have not undergone an orchiectomy and are currently being treated with luteinizing hormone-releasing hormone (LHRH) analogs at the time of consent, therapy must be continued throughout the study.

6.8 Bisphosphonates or other Bone Targeting Agents

Patients cannot have initiated denosumab or bisphosphonate therapy or adjusted bisphosphonate or denosumab dose/regimen within 4 weeks prior to first dose of rucaparib. Patients on a stable denosumab or bisphosphonate regimen are eligible and may continue treatment. Initiation of bisphosphonates or other approved bone targeting agents, if clinically indicated, is allowed, and should not result in study treatment discontinuation unless patient has radiographic evidence of disease progression.

6.9 Other Concomitant Medications

Therapies considered necessary for the patient's well-being may be given at the discretion of the investigator and should be documented on the eCRF. Other concomitant medications, except for analgesics, chronic treatments for concomitant medical conditions, or agents required for life-threatening medical problems, should be avoided. Herbal and complementary therapies are discouraged because of unknown side effects and potential drug interactions, but any taken by the patient should be documented appropriately on the eCRF.

Rucaparib marginally increased digoxin area under the concentration-time curve (AUC) by 20%. Caution should be exercised for patients receiving rucaparib and requiring concomitant medication with digoxin. Patients taking digoxin should have their digoxin levels monitored after starting rucaparib and then regularly per standard clinical practice.

Rucaparib marginally increased the C_{max} and mildly increased the AUC of oral contraceptives (ethinylestradiol and levonorgestrel). No clinically meaningful DDIs are expected for concomitant use of oral contraceptives and rucaparib.

In vitro, rucaparib is a potent inhibitor of MATE1 and MATE2-K, a moderate inhibitor of OCT1, and a weak inhibitor of OCT2. As inhibition of these transporters could decrease metformin renal elimination and decrease liver uptake of metformin, caution is advised when metformin is co-administered with rucaparib.

6.10 General Restrictions

Photosensitivity has been observed in patients treated with rucaparib. Patients should avoid spending time in direct sunlight because they burn more easily during treatment with rucaparib. When outdoors, patients should use typical precautions such as applying sunscreen (sun protection factor 50 or greater) and/or covering exposed skin with clothing and wearing a hat and sunglasses.

7 STUDY PROCEDURES AND METHODS

7.1 Schedule of Assessments

[Table 5](#) summarizes the procedures and assessments to be performed for all patients.

Study procedures and assessments should be performed as close as possible to the scheduled time, but within ± 3 days of the scheduled time unless otherwise stated.

Table 5. Schedule of Assessments for All Patients

	Screening Phase	Treatment Phase (28-day cycles ± 3 days)			Post-treatment Phase			
		Day -28 to Day -1	Day 1	Day 15	Day 1	End of Treatment	28-day Safety Follow-up ^b	Long-Term Follow-up
Procedure^a								
Informed Consent (Section 7.2) ^e	X							
Medical/Oncology History (Section 7.3.1)	X							
Archival Tumor Tissue Sample or Fresh Biopsy ^d	X							
Physical Examination (Section 7.3.4.5) ^e	X	X			X		X	
Vital Signs (Section 7.3.4.3)	X	X	X		X		X	
12-lead ECG (Section 7.3.4.4) ^f	X				X			
Prior/Concomitant Medications/Procedures (Section 7.3.2)	X	X	X		X		X	
Disease Assessment/Tumor Scans ^g (Section 7.3.1)	X				X		X	X
ECOG Performance Status (Section 7.3.4.6)	X	X			X		X	
Hematology (local lab) (Section 7.3.4.2)	X	X	X		X		X	
Serum/Plasma Chemistry (local lab) (Section 7.3.4.2)	X	X	X		X		X	
Urinalysis (local lab) (Section 7.3.4.2)	X	X	X		X		X	
Pregnancy test (WOCBP only; local lab) (Section 7.3.4.2) ^h	X	X			X			
Tumor marker measurement (local lab) ⁱ or PSA measurement (local lab) ^j (Section 7.3.3.2)	X	X			X		X	
Blood Sample for g/s mutation status (central lab) ^k (Section 7.3.6.3)		X						

Table 5. Schedule of Assessments for All Patients

	Screening Phase	Treatment Phase (28-day cycles ± 3 days)			Post-treatment Phase		
		Cycles 1 and 2	Cycles 3+	End of Treatment	28-day Safety Follow-up ^b	Long-Term Follow-up	
Procedure^a	Day -28 to Day -1	Day 1	Day 15	Day 1	End of Treatment	28-day Safety Follow-up^b	Long-Term Follow-up
Blood Sample for ctDNA analysis (central lab) ^f (Section 7.3.6.2)	X	X		X	X	X	
Rucaparib Administration ^m		X		X			
Adverse Events ⁿ (Sections 8.7 and 8.8)	(X)	X	X	X	X	X	
Plasma sample for PK ^o (Section 7.3.5)		X		X			
Tumor Tissue Biopsy (OPTONAL; additional consent required) ^p					X		
Subsequent Treatments, treatment-related SAEs, AESIs, & Survival ^q							X

Abbreviations: AE = adverse event; AESI = adverse event of special interest; BRCA = breast cancer gene; ctDNA = circulating tumor deoxyribonucleic acid; ECG = electrocardiogram; ECOG = Eastern Cooperative Oncology Group; gBRCA = germline BRCA; HRD = homologous recombination deficiency; PK = pharmacokinetics; PSA = prostate-specific antigen; RECIST = Response Evaluation Criteria in Solid Tumors; SAE = serious adverse event; sBRCA = somatic BRCA; WOCBP = women of child-bearing potential.

- a The study visit window in the treatment phase is ± 3 days, unless noted otherwise for a particular assessment. Study visits should take into account the subjects investigational product supply. Only 1 cycle of oral study drug will be dispensed to the subject on Day 1 of each cycle.
- b Follow-up visit should occur 28 days (±7) from the last dose of study drug, or can be performed on the date of discontinuation if that date is at least 28 days from last dose. Chemistry and hematology are only necessary at follow-up visit if toxicities are present. The follow-up visit should be conducted in person.
- c Informed consent may be completed outside the screening window of 28 days prior to study start, as informed consent does not expire, except as required by applicable regulatory requirements or if informed consent is withdrawn by patient.
- d All patients will be required to provide adequate tumor tissue (tumor content > 30% is strongly preferred) for analysis. In the event archival tumor tissue is not available, a screening biopsy sample must be collected and provided to the central laboratory, unless the biopsy procedure is considered unsafe by the investigator or the biopsy site is considered inaccessible. Availability of adequate tumor tissue samples must be confirmed prior to enrollment, but tissue sample may be sent after the patient is enrolled. Submission of a tumor block is strongly preferred. Refer to the Laboratory Manual for detailed sample collection and handling instructions.

- e Height measured at screening and at the EOT visit only.
- f 12-lead ECGs may be repeated at other times as clinically indicated.

- ^g Disease assessments to consist of clinical examination and appropriate imaging techniques per RECIST v1.1 or modified RECIST (for mCRPc) every 8 weeks (\pm 7 days). Other complementary assessments may be performed if required. The same methods used to detect lesions at baseline are to be used to follow the same lesions (including in the CNS), throughout the clinical study. Confirmatory scans should follow at least 4 weeks after the scan at which a response was first documented. For patients who discontinue from study treatment for a reason other than disease progression or death, scans should occur at treatment discontinuation or the 28-day Safety Follow-up Visit if it has been \geq 8 weeks since the last scan or if disease progression was noted on the last scan, and every 8 weeks (\pm 7 days) thereafter, until disease progression, death, loss to follow-up, withdrawal from study, study termination, or initiation of subsequent anticancer treatment. Patients who have been on study at least 18 months will decrease the frequency of tumor assessments to every 16 weeks (\pm 7 days is permitted).
- ^h Female patients of childbearing potential must have a negative serum or plasma hCG pregnancy test result \leq 3 days prior to administration of the first dose of rucaparib. In addition, a serum or plasma hCG pregnancy test must be performed \leq 3 days prior to Day 1 of every cycle during the Treatment Phase and at the time of treatment discontinuation.
- ⁱ Tumor marker measurements per standard of care for a particular tumor type should be performed for patients at screening and on Day 1 of every subsequent cycle, at treatment discontinuation, the 28-day safety follow-up, and as clinically indicated. If a patient discontinues treatment for reasons other than disease progression, then a sample should be taken at the same time as radiological imaging and cDNA sampling.
- ^j All PSA measurements should be performed for patients with prostate cancer by the local laboratory. Serial PSA measurements that show progression at study entry must follow the protocol specification.
- ^k **If sample is not collected on Day 1 of Cycle 1, it should be collected at the next clinic visit.**
- ^l Screening: Day 1 of Cycle 1 through Cycle 6, every other cycle after Cycle 6, and at the End-of-Treatment and 28-day Follow-Up. Refer to the Laboratory Manual for detailed sample collection and handling instructions.
- ^m **First dose of study drug in Cycle 1 should be administered within 3 days of enrollment.** Study treatment continues in 28-day cycles until disease progression, unacceptable toxicity, patient or physician request to discontinue, death, initiation of any other cancer therapy, positive pregnancy test, or termination of the study. Study visit should take into account the patient's rucaparib supply. A quantity of rucaparib sufficient to complete 1 cycle (28 days) should be dispensed to the subject/patient on Day 1 of each cycle.
- ⁿ AEs, SAEs, and AESIs that occur after first administration of study drug through to 28 days after last dose of study drug(s). In addition, SAEs that were related to a screening procedure will also be recorded. Ongoing SAEs, AESIs, or treatment-related Grade 3/4 AEs will be followed to resolution or stabilization. After the Safety Follow-up Visit, only SAEs considered as potentially related to study drug (including serious reports of pneumonitis or similar events, ie, interstitial lung disease, pulmonary fibrosis, acute interstitial pneumonitis, alveolitis, hypersensitivity pneumonitis, and organizing pneumonia, if considered to be related to study drug), and the AESIs of MDS and AML regardless of causality, will be recorded in the eCRF. If a patient discontinues from treatment in the rollover study and begins a subsequent anticancer therapy, the sponsor will terminate collection of SAEs.
- ^o Cycles 2 through 6 only. PK samples should be collected prior to the morning dose on the visit days, and as close as possible to 12 hours after the last dose (even if the morning dose on the specified visit days is not administered). If a new treatment cycle is delayed, the predose PK sample closest to 12 hours after the last dose should still be collected on that visit and should not be collected on Day 1 of the delayed treatment cycle. Refer to the Laboratory Manual for detailed sample collection and handling instructions.

- p An optional tumor biopsy may be collected from patients within 30 days after the time of disease progression or treatment discontinuation. Additional consent is required. Refer to the Laboratory Manual for detailed sample collection and handling instructions.
- q All patients discontinued from treatment, regardless of reason, should be followed for subsequent treatments, secondary malignancy, and survival every 12 weeks relative to the last dose of study drug until death, loss to follow-up, withdrawal of consent from study, or closure of the study. Follow-up can be performed via the telephone and can be completed to coincide with scheduled tumor assessments during this period. Diagnosis of any secondary malignancy requires appropriate documentation (ie, laboratory and/or pathology reports).

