5.6.4 Rucaparib Discontinuation

Rucaparib should be permanently discontinued for any of the following:

- If a patient continues to experience toxicity despite dose reduction steps to the lowest permissible dose or if dosing is interrupted for > 21 consecutive days due to toxicity, treatment with rucaparib should be discontinued, with the following exceptions:
 - Treatment interruption > 21 days may be allowed if approved by the sponsor. Prior to re-initiating treatment for a patient with a treatment interruption lasting > 21 days, the study medical monitor/designee must be consulted. Tumor assessments should continue as per protocol even if treatment is interrupted.
- Confirmed diagnosis of MDS or AML;
- Any AE, laboratory abnormality, or intercurrent illness which, in the judgment of the investigator, presents a substantial clinical risk to the patient with continued oral study treatment dosing; or
- Patient with progressive disease. If a patient receiving study drug has met criteria for radiologic disease progression by RECIST v1.1 criteria (or modified RECIST v1.1 criteria for mCRPC patients), but continues to derive clinical benefit per the investigator, continuation of treatment may be permitted after discussion with the sponsor.

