9.7.2 Adverse Events

Adverse events will be classified using the Medical Dictionary for Regulatory Activities (MedDRA) classification system. The severity of the toxicities will be graded according to the NCI CTCAE v5.0 or later TEAEs are defined as AEs with onset date on or after the date of first dose of study drug until 28 days after the last dose of study drug.

The number and percentage of patients who experienced TEAEs for each system organ class (SOC) and preferred term will be presented. Multiple instances of the TEAE in each SOC and multiple occurrences of the same preferred term are counted only once per patient. The number and percentage of patients with at least one TEAE will also be summarized.

Separate tables will be presented as follows:

- All TEAEs;
- TEAEs by CTCAE grade;
- Grade 3 or greater TEAEs;
- Treatment-related TEAEs
- Serious TEAEs;
- Treatment-related serious TEAEs;
- TEAEs with an outcome of death;
- TEAEs leading to discontinuation of study;
- TEAEs resulting in interruption/delay of study drug; and TEAEs resulting in dose reduction of study drug.

The incidence of TEAEs will be summarized by relationship to study drug (rucaparib) according to the following categories: “treatment-related,” or “not treatment-related”. If a patient experiences multiple occurrence of the same AE, with different relationship categories for the study drug, the patient will be counted once, as a relationship category of treatment related.

If a patient experiences multiple occurrence of the same AE with different toxicity grades, the patient will be counted once for the maximum (most severe) toxicity grade. AEs with a missing toxicity grade will be presented in the summary table with a toxicity grade of “Missing.” For each toxicity grade, the number and percentage of patients with at least 1 TEAE of the given grade will be summarized.

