9.7.3 Clinical Laboratory Evaluations

Clinical laboratory evaluations include the continuous variables for hematology and serum chemistry. The laboratory values will generally be presented in International System of Units (SI). The on-treatment period will be defined as the time from the first dose of rucaparib to 28 days after the last dose of rucaparib or the last Safety Follow-up Visit, whichever is later. Laboratory values collected during the on-treatment period will be included in the summary tables. The laboratory values collected after the on-treatment period will only be presented in the data listings.

The summary of laboratory data will include shift tables based on CTCAE for shifts in grade from baseline to maximum, minimum, and last value during the on-treatment period.

Supporting laboratory data including normal ranges and abnormal laboratory flags will be provided using by-patient listings. Separate listings will be produced for clinically significant laboratory abnormalities (ie, those that meet Grade 3 or Grade 4 criteria according to CTCAE).

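### Laboratory and vital-sign summaries can run past the 28-day TEAE window, and none of these windows stops at the start of subsequent anticancer therapy

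*Combined protocol and SAP*

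**What the plan says.** Section 9.7.3 runs the laboratory on-treatment period from first dose "to 28 days after the last dose of rucaparib or the last Safety Follow-up Visit, whichever is later". Section 9.7.4 uses the same definition for vital signs. Values inside the period enter the summary tables and later values are only listed. The laboratory tables show grade shifts from baseline to the maximum, minimum and last value. The vital-sign tables summarise those same three values and their changes from baseline.

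Section 9.7.2 defines TEAEs as events "with onset date on or after the date of first dose of study drug until 28 days after the last dose of study drug". Table 5, footnote n, ends routine adverse event collection at the same point.

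The date of the safety visit comes from Table 5, footnote b: "Follow-up visit should occur 28 days (±7) from the last dose of study drug, or can be performed on the date of discontinuation", the latter only if that date is at least 28 days after last dose. No latest date is given for this option. Footnote b also makes chemistry and hematology at this visit necessary only when toxicities are present. Section 5.6.4 leaves room for long holds: "Treatment interruption > 21 days may be allowed if approved by the sponsor".

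The protocol does use the start of subsequent anticancer therapy as a cut elsewhere. Section 9.6.2.3 counts only scans before it for progression-free survival, and Section 3.1.4 stops SAE collection at that point, apart from MDS and AML.

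**The concern.** Two gaps follow from these definitions.

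First, the safety tables need not cover the same period. A new Grade 3 laboratory value on day 33, drawn at a permitted visit, enters the rucaparib shift table. An adverse event starting that day is not a TEAE. Under Section 8.7 it is not routinely recorded either, unless it is a potentially related SAE or a case of MDS or AML.

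Second, nothing stops values drawn after next-line treatment from being summarised as on rucaparib. A cytopenia caused by the next regimen could set a worst-grade shift. SAE collection for that patient may already have stopped for the very reason that new therapy had begun.

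Clinical laboratory abnormalities are a named safety endpoint in Section 9.7, and the single-arm design has no control group in which an artefact of the window would show. What is at stake is how the descriptive laboratory and vital-sign tables are read. No efficacy result, futility decision or error rate depends on it.

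**Working it through.** The plan states no figure to reproduce. The check is day arithmetic on the stated windows, counting from last dose as day 0.

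**Inputs**
- Laboratory and vital-sign window end: max(28, v), where v is the day of the Safety Follow-up Visit (Sections 9.7.3 and 9.7.4).
- TEAE window end: day 28 (Section 9.7.2).
- Permitted v: 28 − 7 = 21 to 28 + 7 = 35, or the discontinuation date if that is day 28 or later (Table 5, footnote b).
- Half-life: 11 to 29.8 hours (Section 1.1.5).

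**Excess of the laboratory and vital-sign window over the TEAE window = max(28, v) − 28**

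| Visit day v | Laboratory and vital-sign end | TEAE end | Excess |
|---|---|---|---|
| 21 to 28 | 28 | 28 | 0 days |
| 29 to 35 | 29 to 35 | 28 | 1 to 7 days |
| Discontinuation date D, later than day 28 | D | 28 | D − 28, no stated limit |

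Of the 15 days from 21 to 35, 7 give an excess. The largest is 7 days, or 7/28 = 25% of the post-dose period.

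**The late-discontinuation row.** A hold that ends in resumed dosing creates no excess, because the last dose then falls later. Only a hold that ends in discontinuation matters. As an illustration, take the 42-day interruption that Section 5.6.2 describes for persistent anemia. If the patient is discontinued on day 42 and the visit is held that day, the excess is 42 − 28 = 14 days. Any blood counts from days 29 to 42 would then be tabulated.

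**Next-line therapy.** Set side by side, Section 9.6.2.3 (scans) and Section 3.1.4 (SAE collection) have a cut at new therapy, while Sections 9.7.2, 9.7.3 and 9.7.4 have none. The gap is thus present both before day 28, for all three data types, and from day 29 on, for laboratory values and vital signs.

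**Does the half-life separate the two windows?** Half-lives elapsed = days × 24 / half-life.
- Day 28: 672/29.8 = 22.6 to 672/11 = 61.1.
- Day 35: 840/29.8 = 28.2 to 840/11 = 76.4.

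Day 28 is already as far off drug as day 35 for practical purposes. The half-life gives no reason to criticise one window and accept the other. The case rests on the mismatch and on the missing cut at new therapy.

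**The case against.** Including the scheduled safety visit in the summary period is an explicit and defensible convention. Several further arguments limit the point.

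- **Size.** Under the ±7-day rule the excess is small and often zero. Because footnote b requires hematology and chemistry only with toxicity, many late visits may add no laboratory value. This stands, with one qualification: the late values that do exist are then selected toward patients with toxicity. Vital signs carry no such condition.
- **TEAEs go by onset date.** Toxicity that began by day 28 remains a TEAE, so the tables diverge only for new onset afterwards. This stands.
- **The two problems barely overlap.** A reader might infer that the open-ended window fills the tables with next-therapy values. The documents do not support that. Starting another cancer therapy itself ends treatment (Table 5, footnote m), and Section 6.2 bars other anticancer therapy on study apart from palliative radiotherapy. A patient on hold until a late discontinuation visit is therefore not expected to be on the next regimen.
- **Off-drug is not the same as unrelated.** A reader might also infer from the half-life that late values cannot reflect rucaparib. Plasma clearance does not bound marrow toxicity, and Section 5.6.2 itself plans for anemia that persists after 42 days of interruption. Moving such values out of the tables could hide persistent toxicity unless they are shown clearly in listings.
- **Further detail may exist.** Section 9.1 defers detail to a separate SAP, which is not in the text reviewed. It might add a rule, but it would have to depart from explicit protocol wording to do so.

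These arguments reduce the size of the point. They do not remove the difference between the window definitions or the absence of a rule at subsequent therapy.

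**Conclusion.** The point holds and is minor. As written, laboratory and vital-sign values after day 28 can enter the rucaparib summaries when an event starting on the same day would not be a TEAE. No rule removes values or events that follow the start of next-line therapy.

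The excess is 0 to 7 days under the visit window and unlimited in the text for a visit at a late discontinuation date. It has an effect only if a sample is drawn in the extra period, or after new therapy, and that value becomes the maximum, minimum or last one. The documents give no means of estimating how often this would happen.

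It would go too far to say that next-therapy values are routinely tabulated as rucaparib data, or that following the plan necessarily distorts the tables. The text permits this; it does not make it certain. The conclusion assumes that the separate SAP adds no overriding window.

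**What to change.** Define one analysis window for TEAEs, laboratory values and vital signs in Sections 9.7.2 to 9.7.4: from first dose to the earlier of 28 days after last dose and the day before the first subsequent anticancer therapy. Show everything later in listings, and state there that persistent toxicity during long holds is included.

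Day 28 suits the common end because routine adverse event collection stops there: "AEs, SAEs, and AESIs that occur after first administration of study drug through to 28 days after last dose of study drug(s"). Lengthening the TEAE window instead would call for events that are not routinely collected. Capping the laboratory window at day 35 would leave the day 29 to 35 mismatch in place. Cutting only laboratory values and vital signs at new therapy would create a fresh mismatch with TEAEs before day 28.

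The cost is a few sentences of wording. Subsequent treatments are already followed under Section 3.1.4, and the progression-free survival rule already needs their start date. The downside is that a few late values and events move from tables to listings.
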